10.6. Appendix 6: Derived and Transformed Data

10.6.1. General

Multiple Measurements at One Time Point

 There are no scheduled multiple measurements, however, if multiple measurements are recorded at a given time point the following process will be followed, unless a process for selection of the measurement for the visit is specified. Mean of the measurements will be calculated and used in any derivation of summary statistics but if listed, all data will be presented. If there are two values within a time window the value closest to the target day for that window will be used. If values are the same distance from the target then the mean will be taken. Subjects having both High and Low values for Normal Ranges at any post-baseline visits for safety parameters will be counted in both the High and Low categories of “Any visit post-baseline” row of related summary tables.
Study Day

Calculated as the number of days from first mepolizumab dose:
 
 Ref Date = Missing Study Day = Missing Ref Date < First mepolizumab dose Study Day = Ref Date - First dose of mepolizumab Ref Date ≥ First mepolizumab dose Study Day = Ref Date - (First dose of mepolizumab) + 1

10.6.2. Study Population

Demographics
Age

 Only year of birth was collected for subjects; actual birth data was not collected. GSK standard IDSL algorithms will be used for calculating age where birth date of all subjects will be imputed as ‘30th June’. Birth date will be presented in listings as ‘YYYY’. Each subject’s derived age will be calculated as an integer value based on their imputed date of birth relative to the date of the subject’s screening visit (Visit 1) $[(30^{\text{th}} \text{ June of the year of birth reported on eCRF} - \text{date of Screening})/365.25]$ Derived age may not represent the actual age of a subject at entry to the study All tables which include age will describe this as “derived age” and will include a footnote to indicate that a) actual age was not collected, b) age was derived using a value of 30th June for birth date and c) this may not represent the actual age of a subject at entry to the study.
Body Mass Index (BMI)

 Calculated as $\text{Weight (kg)} / [\text{Height (m)}]^2$
Disease parameters
Percent Predicted FEV1

 FEV1 % of predicted normal will be derived using the Global Lung Function Initiative 2012 look-up tables [Quanjer, 2012]

Disease parameters
FEV₁/FVC Ratio

 Pre- and post-bronchodilator FEV₁/FVC ratio will be calculated as the ratio of the FEV₁ and FVC values.
Blood Eosinophils

 Blood eosinophil count will be log transformed prior to analysis. Summary statistics will include geometric mean and a measure of spread (SD or SE) on the natural log scale. If a blood eosinophil count of zero is reported, it will be imputed with half of the lowest possible blood eosinophil count, where applicable, prior to log transforming the data (Note: this imputation has typically been $0.5 * 0.01 \text{ GI/L} = 0.005 \text{ GI/L}$ for previous mepolizumab studies).
Categories defined based on databased information regarding blood eosinophil counts in the previous 12 months and observed blood eosinophil counts at the Screening visit.

 Historical and Screening: Blood eosinophil count ≥ 300 cells/μL in previous 12 months and ≥ 150 cells/μL at Screening Historical Only: Blood eosinophil count ≥ 300 cells/μL in previous 12 months and < 150 cells/μL at Screening Screening Only: Blood eosinophil count < 300 cells/μL or missing or unknown in previous 12 months and ≥ 150 cells/μL at Screening
Baseline OCS daily dose

 Only corticosteroids administered via oral, intravenous (IV) and intramuscular (IM) routes are to be considered when calculating a subject's total daily prednisone/prednisolone asthma maintenance dose at baseline. All steroids administered via a sublingual route will also be considered as oral. The corticosteroid conversion factors shown below will be used, regardless of the route of administration, to scale each corticosteroid dose to a prednisone equivalent dose. These three routes of administration (oral, IV and IM) are to be considered equivalent as it has been noted that the bioavailability of methylprednisolone is considered to be roughly equivalent following administration as an oral, IV or IM steroid.

Standardised Medication Name	Scaling Factor
Betamethasone	8.33
Betamethasone Dipropionate	8.33
Betamethasone Sodium Phosphate	8.33
Cortisone	0.2
Cortisone Acetate	0.2
Cortivazol	17
Deflazacort	0.833
Dexamethasone	6.67
Dexamethasone Sodium Phosphate	6.67
Fludrocortisone Acetate	0
Hydrocortisone	0.25
Hydrocortisone Sodium Succinate	0.25
Hydrocortisone Sodium Phosphate	0.25

Standardised Medication Name	Scaling Factor
Meprednisone	1
Methylprednisolone	1.25
Methylprednisolone Acetate	1.25
Methylprednisolone Sodium Succinate	1.25
Methylprednisone	1.25
Methylprednisone Acetate	1.25
Methylprednisolone Sodium Succinate	1.25
Methylprednisone	1.25
Methylprednisone Acetate	1.25
Prednisolone	1
Prednisolone Acetate	1
Prednisolone Hemisuccinate	1
Prednisolone Sodium Succinate	1
Prednisone	1
Prednisone Acetate	1
Triamcinolone	1.25
Triamcinolone Acetonide	1.25

Extent of Exposure (Days)

 • Within each study part (Part A/Part B) the number of days of total exposure to mepolizumab will be calculated based on the formula: $\text{Duration of Exposure} = \text{Last dose of mepolizumab} - (\text{First dose of mepolizumab}) + 29$ • Within each study part (Part A/Part B) the number of days of exposure to specific mepolizumab doses will be calculated as follows: Subjects receiving mepolizumab 40mg SC only: $\text{Duration of Exposure} = \text{Last dose of mepo 40mg} - (\text{First dose of mepo 40mg}) + 29$ Subjects receiving mepolizumab 100mg SC only: $\text{Duration of Exposure} = \text{Last dose of mepo 100mg} - (\text{First dose of mepo 100mg}) + 29$ Subjects receiving mepolizumab 40mg SC and mepolizumab 100mg (Part B only): $\text{Duration of 40mg Exposure} = \text{First dose of mepo 100mg} - (\text{First dose of mepo 40mg}) + 1$ $\text{Duration of 100mg Exposure} = \text{Last dose of mepo 100mg} - (\text{First dose of mepo 100mg}) + 28$ • Subjects who never received a mepolizumab dose will be categorised as having zero days of exposure. • The extent of exposure will also be summarised as the number of study treatments administered within each study part (Part A/Part B).

10.6.3. Subject Disposition**Subject Disposition**

- It is an eligibility requirement that subjects must complete all study assessments up-to and including Visit 8 (and received all 3 doses of investigational product) in Part A before entering study Part B
- Subjects who complete Part A will not have a disposition (study part completion/withdrawal) record created at the completion of Part A. Instead a derived disposition record will be required utilising the Part B status (RLSTUDY) flag. A disposition record will be available for Part B.

10.6.4. Safety**AEs of Special Interest**

Section 8.2.1.1 provides a full list of AEs of special interest for this compound.

AESIs of anaphylaxis reactions, systemic reactions, and local injection site reactions are collected via targeted eCRF. Systemic reactions with preferred terms such as injection related reaction or administration related reaction will be considered non-allergic reactions; those with other preferred terms will be considered allergic/hypersensitivity reactions.

The AESIs of opportunistic infections, malignancies, serious CVT events and serious ischemic events will be identified from a list of relevant preferred terms maintained within a project level reference dataset; created based on the latest version of the MedDRA dictionary available at the time of database freeze for this study (See Program Safety Analysis Plan for additional details).

ECG Parameters**RR Interval**

All ECG parameters required in this study will be databased, and therefore, further derivations will not be performed by Stats and Programming. The definitions of these parameters are given in this section.

- If RR interval (msec) is not databased, then RR can be derived as :
[1] If QTcB is machine read & QTcF is not provided, then :

$$RR = \left[\left(\frac{QT}{QT_{cB}} \right)^2 \right] * 1000$$

- [2] If QTcF is machine read and QTcB is not provided, then:

$$RR = \left[\left(\frac{QT}{QT_{cF}} \right)^3 \right] * 1000$$

- If ECGs are manually read, the RR value should be a collected value and will not be derived.

Corrected QT Intervals

- When not databased, corrected QT intervals by Bazett's (QTcB) and Fredericia's (QTcF) formulas will be calculated, in msec, depending on the availability of other measurements.
- If RR interval (msec) is provided then missing QTcB and/or QTcF will be derived as :

$$QTcB = \frac{QT}{\sqrt{\frac{RR}{1000}}}$$

$$QTcF = \frac{QT}{\sqrt[3]{\frac{RR}{1000}}}$$

- Individual maximum QTc(F) and QTc(B) values will also be summarised by treatment group for each scheduled study visit to show the number of subjects with maximum values (msec) in the following categories:
 - <= 450
 - 450 < to <= 480
 - 480 < to <= 500
 - > 500
- Additionally, individual maximum changes from baseline in QTc(F) and QTc(B) values will be summarised by treatment group for each scheduled study visit to show the number of subjects with maximum changes (msec) in the following categories:
 - < -60
 - ≥ -60 to < -30
 - ≥ -30 to < 0
 - ≥ 0 to < 30
 - ≥ 30 to < 60
 - ≥ 60

Laboratory Parameters

- If a laboratory value which is expected to have a numeric value for summary purposes, has a character value starting with '<x' or '>x' (or indicated as less than x or greater than x in the comment field), the number of significant digits in the observed values will be used to determine how much to add or subtract in order to impute the corresponding numeric value.
 - Example 1: 2 Significant Digits = '< x' becomes x - 0.01
 - Example 2: 1 Significant Digit = '> x' becomes x + 0.1
 - Example 3: 0 Significant Digits = '< x' becomes x - 1
- If a laboratory value is missing due to being below the limit of quantification (BLQ) then the value will be imputed as half the lower limit of quantification for that measure (i.e. the lowest observed value for that measure within the entire study database).

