10.7.2. Handling of Missing Data

Element	Reporting Detail
General	
 Missing data occurs when any requested data is not provided. These data will be indicated by the use of a "blank" in subject listing displays. Unless all data for a specific visit are missing in which case the data is excluded from the listing. Answers such as "Not applicable" and "Not evaluable" are not considered to be missing data and should not be displayed as missing. PK concentrations reported as Not Quantified (NQ)/Below the Lower Limit of Quantification (BQL) will be handled as per standard GSK practice. Below the limit of quantification (BLQ) is not missing data and must be displayed as such and included in all listings and summaries

Element	Reporting Detail
	
 If a blood eosinophil count of zero is reported, it will be imputed with half of the lowest possible blood eosinophil count, where applicable, prior to log transforming the data (Note: this imputation has typically been $0.5 * 0.01$ GI/L = 0.005 GI/L for previous mepolizumab studies). The ACQ-7 score will be considered as missing if <6 items of the questionnaire are completed at a visit. ACQ-7 Responder/Non-responder category will be missing if the overall ACQ-7 score is missing. The ACQ-5 score will be considered as missing if <4 items of the questionnaire are completed at a visit. ACQ-5 Responder/Non-responder category will be missing if the overall ACQ-5 score is missing. Missing values will not be imputed for any of the other endpoints.
Outliers	
 Any subjects excluded from the summaries and/or statistical analyses will be documented along with the reason for exclusion in the clinical study report.
Sensitivity analysis	
 No sensitivity analyses are planned for this study. However as detailed in Section 7, exploratory sensitivity analyses may be considered if there are protocol deviations that may potentially affect the PK and/or PD endpoints. If any sensitivity analyses are performed the details will be documented in the clinical study report.

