No.	Population	IDSL / TST ID / Example Shell	Title	Programming Notes	Deliverable [Priority]
IL-5					
2.24.	PDo		Summary of IL-5 (Part A)	Log transformed with geometric mean, include ratio to baseline See format of Efficacy Table 6.71 (MEA115588 'final' reporting effort)	SAC1

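### The SAP sets the quantification limit of a laboratory assay at the lowest observed value, so a below-limit result can be imputed above the true limit; its two below-limit rules have no precedence and IL-5 has no named rule.

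*SAP*

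**What the plan says.** SAP 10.6.4 (Laboratory Parameters) puts two rules for below-limit results side by side.

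- **One-unit rule.** It applies when a result that should be numeric "has a character value starting with '<x' or '>x' (or indicated as less than x or greater than x in the comment field"). In that case "the number of significant digits in the observed values will be used to determine how much to add or subtract". The below-limit examples are "Example 1: 2 Significant Digits = '< x' becomes x - 0.01" and "Example 3: 0 Significant Digits = '< x' becomes x - 1".
- **Half-limit rule.** It opens: "If a laboratory value is missing due to being below the limit of quantification (BLQ) then the value will be imputed as half". The quantity to be halved is then explained: the imputed value is "half the lower limit of quantification for that measure (i.e. the lowest observed value for that measure within the entire study database").

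The SAP does not say which rule wins if both could apply, or how the laboratory will transmit a BLQ result. SAP 10.7.2 states: "Below the limit of quantification (BLQ) is not missing data and must be displayed as such and included in all listings and summaries". The same section closes by ruling out imputation for endpoints it has not named.

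IL-5 is an outcome of the PDo population (SAP Section 4) and exploratory in SAP Table 7. The programming note for Table 2.24 reads "Log transformed with geometric mean, include ratio to baseline", and Figure 2.23 plots that ratio. No BLQ rule names IL-5. By contrast, zero eosinophil counts have their own rule (SAP 10.6.2 and 10.7.2), and so do BLQ drug concentrations (SAP 10.7.2 and 10.8.1).

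**The concern.** The lower limit of quantification (LLOQ) belongs to the assay and is fixed by validation. The lowest quantified value in a study is at or above it and depends on which children were sampled. Treating the two as the same thing has three consequences. The imputed value can exceed the limit that the sample is known to lie below. It can change as data accumulate. And if every result for an analyte is BLQ, there is no quantified value to halve.

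The two rules also split results by how they are recorded, not by what was measured. The half-limit rule is triggered by a value being missing, a label that SAP 10.7.2 rejects for BLQ results. A programmer would have to settle this after seeing the data.

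IL-5 is the most exposed variable because a logarithm needs a positive number. Each BLQ result must be replaced or dropped, and the SAP does not say which.

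**Working it through.** No figure in either document rests on these rules, so there is nothing to reproduce. The documents give no IL-5 LLOQ, reporting precision, recording format or BLQ rate; the values of x, d and L below are illustrations.

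**Inputs and formulas.** Let x be the reported limit, d the number of decimals (as the SAP examples use the term digits) and L the lowest observed value.

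- One-unit rule: x − 10^−d.
- Half-limit rule as written: L/2.
- Gap for one result: (x − 10^−d) ÷ (L/2).

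**1. Same result, two recordings, with L = x.**

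| Reported | One-unit | Half-limit | Gap |
|---|---|---|---|
| `<1` | 0 | 0.5 | log undefined |
| `<2` | 1 | 1 | 1.00 |
| `<5` | 4 | 2.5 | 1.60 |
| `<1.0` | 0.9 | 0.5 | 1.80 |
| `<1.00` | 0.99 | 0.50 | 1.98 |
| `<10.00` | 9.99 | 5.00 | 1.998 |

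**2. Lowest observed value above the true limit (LLOQ = 1.00, d = 2, one-unit value 0.99).**

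| L | Half-limit as written | Above the LLOQ? | Gap |
|---|---|---|---|
| 1.00 | 0.50 | no | 1.98 |
| 1.50 | 0.75 | no | 1.32 |
| 2.50 | 1.25 | yes | 1.26, reversed |
| 3.00 | 1.50 | yes | 1.52, reversed |
| 5.00 | 2.50 | yes | 2.53, reversed |

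L/2 exceeds the LLOQ exactly when L > 2 × LLOQ.

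**3. Change between reports.** SAP 3.1 and 3.2 make the Part A outputs final and do not rerun them. SAP 10.5.2.1 uses the same pre-dose baseline in both parts, and Part B Tables 3.97 and 3.99 show baseline values again. As the database grows, L can only stay or fall. If L went from 2.50 at Part A to 1.50 at the end, one child's BLQ baseline would be 2.50/2 = 1.25 in the first report and 1.50/2 = 0.75 in the second. This applies to safety analytes only: the Part B schedule (Protocol Table 4) has no IL-5 sample.

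**4. IL-5, if SAP 10.6.4 is applied to it.** Samples are taken at Weeks 0 and 12 only (Protocol Table 3). Suppose a share p of subjects is BLQ at one time point only, the same one for all of them. Switching rules then multiplies the geometric mean ratio by gap^p. With L = x and the limiting gap of 2:

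- p = 10%: 2^0.10 = 1.07
- p = 25%: 2^0.25 = 1.19
- p = 50%: 2^0.50 = 1.41
- p = 100%: 2.00
- one subject among the 20 planned evaluable: 2^(1/20) = 1.035

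A subject BLQ at both visits has a ratio of 1 under either rule. Subjects BLQ at Week 0 only and at Week 12 only pull in opposite directions.

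**The case against.** A reader might infer that the two rules contradict each other. The text does not go that far. One is triggered by a character result and the other by a missing value, and a central laboratory may well report each assay in one format throughout. One rule would then apply to every subject and visit for that analyte. What remains is an overlap without precedence, which depends on a format that the SAP leaves open.

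The step to IL-5 is also open to challenge. Both rules stand under Safety, whereas IL-5 is reported among the efficacy tables, is absent from the laboratory list in Protocol Table 5, and is not an endpoint in Protocol Section 3. Its row sits under Laboratory Assessments in the visit schedule, which gives some support, but the SAP never makes the link. Read literally, the no-imputation sentence in SAP 10.7.2 could mean that BLQ IL-5 results are dropped. This objection stands, so the IL-5 figures are conditional. The gap does not close, however: a log-scale display has no stated rule for BLQ results.

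The mismatch with SAP 10.7.2 can be called mild. That sentence follows one on drug concentrations, and imputing a value does let a BLQ result enter the summaries. Its wording is not limited to drug concentrations, though, and it still denies the label that triggers the half-limit rule.

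Finally, half the LLOQ is itself a convention. That is true, but it always lies below the limit and does not depend on the sample.

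None of these objections rescues the equation of the LLOQ with the lowest observed value.

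**Conclusion.** The point holds as a minor correction to a stated rule. Followed literally, SAP 10.6.4 imputes a BLQ result above the assay limit whenever the lowest observed value exceeds twice that limit, and it can give one child's safety baseline two values in two reports. The one-unit rule can return 0. These conclusions need only the SAP text and arithmetic; whether either situation will arise cannot be told from the documents.

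The size for IL-5 is less certain. It assumes that the safety rules are carried over, that the lowest observed value equals the LLOQ, and a BLQ rate that is not given. On those terms the shift is about 1.07-fold at 10% and 1.41-fold at 50%.

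A reader might infer that the IL-5 ratio can change by up to two-fold. The documents do not support that figure. At group level it would need every subject to be BLQ at one time point and none at the other. For a single value it is not a bound either: with a limit of 1.00 and a lowest value of 5.00 the gap is 2.53-fold.

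The effect is confined to exploratory IL-5 and safety laboratory summaries. The eosinophil and PK endpoints have their own rules.

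**What to change.** In SAP 10.6.4:

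- Delete the gloss that equates the LLOQ with the lowest observed value.
- Impute half the assay's validated LLOQ for any result below quantification, whether it arrives as `<x`, as BLQ or as a blank with a comment.
- Keep the one-unit rule for `>x` and for any `<x` that is not a quantification limit.
- State that the rule covers IL-5.

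In SAP 10.7.2, align the wording so that a BLQ result is not called missing in one section and not missing in another, and so that the no-imputation sentence does not exclude IL-5. In Table 2.24, show the number of BLQ results at each visit. Leave the eosinophil zero rule and the PK rules unchanged.

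The cost is a few sentences, one count column, and obtaining the validated limits from the laboratories. No new data are needed.

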10.6.5. Efficacy

Patient Reported Outcomes/Questionnaires

ACQ-7
 
 • The questionnaire includes 7 items; and requires a 1 week recall (for items on symptoms and rescue inhaler use). The ACQ has a multidimensional construct assessing symptoms (5 items administered by clinic staff to the child) and rescue bronchodilator use (query to child or parent), and FEV1 % predicted (1 item) completed by clinic staff. • Each question on the ACQ-7 is scored on a 7-point scale from 0 = no impairment to 6 = maximum impairment. The questions are equally weighted and the ACQ-7 score will be the mean of the 7 questions, thus giving a score between 0 (totally controlled) and 6 (severely uncontrolled) [Juniper, 2010; Juniper, 1999; Juniper, 2005]. • A subject will be deemed a responder if the subject has a ≥ 0.5 reduction in ACQ score from Baseline • If a subject does not complete 1 of the 7 questions at a visit, then the ACQ-7 score will be the mean of the responses to the remaining 6 questions at that visit. • If a subject does not complete more than 1 of the 7 questions at a visit, then their ACQ-7 score will be set to missing at that visit. • ACQ-7 Responder/Non-responder category will be missing if the overall ACQ-7 score is missing.

ACQ-5
 
 • The ACQ-5 questionnaire consists of the 5 symptoms questions (Q1-Q5) of the ACQ-7 requiring a 1 week recall. • Each question on the ACQ-5 is scored on a 7-point scale from 0 = no impairment to 6 = maximum impairment. The questions are equally weighted and the ACQ-5 score will be the mean of the 5 questions, thus giving a score between 0 (totally controlled) and 6 (severely uncontrolled) [Juniper, 2010; Juniper, 1999; Juniper, 2005]. • A subject will be deemed a responder if the subject has a ≥ 0.5 reduction in ACQ score from Baseline • If a subject does not complete 1 of the 5 questions at a visit, then the ACQ-5 score will be the mean of the responses to the remaining 4 questions at that visit. • If a subject does not complete more than 1 of the 5 questions at a visit, then their ACQ-5 score will be set to missing at that visit. • ACQ-5 Responder/Non-responder category will be missing if the overall ACQ-5 score is missing.

C-ACT
 
 • The C-ACT is a 7-question, 2-part questionnaire, with items one through 4 to be completed by the child (with assistance from a caregiver, as needed) and items 5 to 7 to be completed by the caregiver [Liu, 2010; Liu, 2007]. • The scores for each of the questions will be summed to derive the total score for that subject at that visit. If the response to any question is missing then the C-ACT total score is also set to missing.

Exacerbations

An exacerbation of asthma as defined as:
 
Worsening of asthma which requires use of systemic corticosteroids¹and/or hospitalisation and/or Emergency Department (ED) visits.
 
 ¹For all subjects, i.v. or oral steroid (e.g., prednisone) for at least 3 days or a single IM CS dose is required. For subjects on maintenance systemic corticosteroids, at least double the existing maintenance dose for at least 3 days is required. 
Exacerbations separated by less than 7 days will be treated as a continuation of the same exacerbation. Each individual exacerbation will be listed.

